10.2 Data Collection

Data collection requirements are summarized in Table 4 below.

Table 4: Data collection and study procedure requirements at subject visits

Study Procedure	Enrollment	Baseline	MRI visit	1 month post MRI	Unscheduled Visit	Study Exit
IC	×					
Inclusion/exclusion assessment	×					
Physical Exam, Demographics, Cardiovascular Medical History, device information		×				
Pre MRI check			×			
Device interrogation			× *	×	×	
MRI scan			×			
Post MRI check			×			
Medication				As they occur **		
AEs				As they occur		
DDs				As they occur		
Study deviations				As they occur		

* Device interrogation performed twice at MRI visit (pre MRI scan and post MRI scan)

** Only collect AE related medication in this study

10.3 Scheduled Follow-up Visit Windows

After receiving notice of successful implantation/device application, Medtronic will provide the target dates and windows for each visit to the study site if applicable. Should a subject miss a visit or the visit fall outside the pre-specified window, a study deviation must be reported and the original follow-up schedule maintained for subsequent visits.

Medtronic Business Restricted

China CIED 3.0T MRI Performance Study Clinical Investigation Plan

MDT23009

Version 2.0

Page 23 of 60

Medtronic

Data analyses include follow-up visits, regardless of whether the visit occurs within the window. Therefore, a late visit is preferred over a missed visit but must be accompanied by a deviation report. Follow-up visit windows are listed in Table 5 and are based on days post MRI scan.

Table 5: Scheduled follow-up visit window

Study Follow-up Visit	Window(Calculated days post-MRI visit)		
	Window Start (days post-MRI)	Target (days post- MRI)	Window End (days post-MRI)
MRI visit*	-	-	-
1 month post MRI	30	30	56

*highly recommend completing the MRI scan within 30 days after baseline visit

10.4 Subject Consent

Informed consent is defined as a legally effective documented confirmation of a subject's voluntary agreement to participate in a particular study after information has been given and explained to the subject on all aspects of the study that are relevant to the subject's decision to participate. This process includes obtaining an IC form as required by law that has been approved by the study site's EC and signed and dated by the subject. A subject may only consent after information has been given and explained to the subject on all aspects of the clinical investigation that are relevant to the subject's decision to participate.

Prior to enrolling subjects, the IC site must be approved by the EC. The document(s) must be controlled (i.e. versioned and dated) to ensure it is clear which version(s) were approved by the EC. Any adaptation of the sample IC must be reviewed and approved by Medtronic and the EC reviewing the application prior to enrolling subjects.

The investigator must notify the subject of any significant new findings about the study that become available during the course of the study which are pertinent to the safety and well-being of the subject, as this could impact a subject's willingness to participate in the study. If relevant, consent may be requested from subjects to confirm their continued participation.

Prior to initiation of any study-specific procedures, IC must be obtained from the subject. Likewise, privacy or health information protection regulation may require subjects to sign additional forms to authorize study sites to submit subject information to the study sponsor. The IC process must be conducted by the principal investigator or an authorized designee, and the IC Form in a language he/she is able to read and understand. The process of IC must be conducted without using coercion or undue improper influence on or inducement of the subject to participate by the investigator or other study site personnel. The IC process shall not waive or appear to waive subject's legal right. The language used shall be as non-technical as possible and must be understandable to the subject and the impartial witness, where applicable.

The subject must have ample time and opportunity to read and understand the IC form, to inquire about details of the study, and to decide whether or not to participate in the study. All questions about the study should be answered to the satisfaction of the subject.

Medtronic Business Restricted

China CIED 3.0T MRI Performance Study Clinical Investigation Plan

MDT23009

Version 2.0

Page 24 of 60

Medtronic

When the subject decides to participate in the study, the IC must be signed and personally dated by the subject and investigator or authorized designee, as required by the IC, and ensured by the principal investigator or his/her authorized designee.

A copy of the IC signed and dated as required by law, must be provided to the subject and his/her authorized designee.

If the IC is obtained the same day the subject begins participating in study-related procedures, it must be documented in the subject's case history that consent was obtained prior to participation in any study-related procedures. It is best practice for the IC process to be documented in the subject's case history, regardless of circumstance.

In the event the subject cannot read and/or write, witnessed (impartial witness) IC will be allowed, provided detailed documentation of the process is recorded in the subject's case history and the witness signs and dates the IC. The IC should document the method used for communication with the prospective subject and the specific means by which the prospective subject communicated consent to participate in the study.

The original of the signed IC must be filed in the hospital/clinical chart and/or with the subject's study documents.

The IC must be available for monitoring and auditing. Any Medtronic Field personnel who support the MRI procedure must be able to review the subject's signed and dated IC and verify its completeness prior to proceeding with the implant/download. In the event the Medtronic Field personnel identify IC as being incomplete, the MRI procedure will not be allowed to occur until the consent of the subject can be adequately and appropriately obtained.

10.5 Enrollment

A subject is considered enrolled when the consent process has been finalized. The date the subject signed the IC must be documented in the subject's medical records. Confirmation of Inclusion/Exclusion Criteria of subject will be performed by investigator at enrollment visit. Enrollment can be a stand-alone visit or can occur on the same day as the baseline visit. Once consent is obtained, report adverse events, device deficiency, study deviations and subject exits as they occur.

10.6 Baseline

The baseline visit can be a stand-alone visit or can be performed on the same day as the MRI visit.

The following information is required to be collected at the baseline visit:

- Physical Exam: a basic physical exam will be performed, including height and weight
- Demographics
- Relevant cardiovascular medical history
- Device /lead information
- Adverse Event assessment
- Device Deficiency assessment

10.7 MRI visit

The following information is required to be collected at the MRI visit:

Medtronic Business Restricted

China CIED 3.0T MRI Performance Study Clinical Investigation Plan

MDT23009

Version 2.0

Page 25 of 60

Medtronic

- Pre MRI check*(appendix A)
- Pacing Threshold Testing Pre-MRI
- Sensing Testing Pre-MRI
- Impedance Testing Pre-MRI
- Final device Interrogation Pre-MRI
- Pre-MRI System Checks
- Device Programming Pre-MRI
- MRI Scan Procedure **
- Device Programming Post-MRI
- Pacing Threshold Testing Post-MRI
- Sensing Testing Post-MRI
- Impedance Testing Post-MRI
- Final device Interrogation Post-MRI
- Adverse Event assessment
- Device Deficiency assessment

*The subject unmet the pre MRI checklist will exit the study

**A cardiac resuscitation-trained individual must be present during the MRI scan.

10.8 Scheduled Follow-up Visits

Scheduled visits will occur at 1 month post MRI at study site.

The following information is required to be collected at follow-up visits:

- Pacing Threshold Testing
- Sensing Testing
- Impedance Testing
- Final device Interrogation
- Adverse Event assessment
- Device Deficiency assessment

10.9 Unscheduled Follow-up Visits

An Unscheduled follow-up visit is defined as any non-standard of care visit by the subject to the study site due to the 3.0T MRI scan before subject completed CIP-required exit visits.

The following information is required to be collected at unscheduled follow-up visits:

- Document any adverse events and/or device deficiencies on the associated eCRFs, as applicable.
- Where possible, initial (beginning of the visit) and final (end of the visit) device interrogation data should be collected

Medtronic Business Restricted

- If electrical testing is conducted, save and print the Test Report and store at site and send a copy to Medtronic if possible

10.10 Recording Data

Data entered must be traceable to source documents. Source documentation is defined as the first time data appear, and may include original documents, data, and records (e.g., hospital records, clinical and office charts, procedure reports, laboratory notes, memoranda, subjects' diaries or evaluation checklists, pharmacy dispensing records, recorded data from automated instruments, copies or transcriptions certified after verification as being accurate copies, microfiches, photographic negatives, microfilm or magnetic media, X-rays, subject files, device data and records kept at the pharmacy, at the laboratories and at medico-technical departments involved in the study).

In general, eCRFs (or paper copies) may not serve as source documents. An exception may be the completion of QoL Questionnaires and clinical scales. Source documentation for data elements not routinely captured in medical records may vary from study site to study site; the study site may use source document worksheets if identified as source documents.

The investigator must ensure the availability of source documents from which the information on the eCRFs was derived. The type and location of source documents should be documented.

The source documents must be made available for monitoring or auditing by Medtronic's representative or representatives of the competent authorities and other applicable regulatory agencies.

The CRF may be considered source for the following data collection elements:

- Enrollment Notification
 - Study site assigned subject reference
- Baseline
 - Administrative information
- AE eCRF
 - Date study site became aware of event
 - Relatedness of adverse event
- Medication eCRF
 - Medication related with AE
- DD eCRF
 - Date study site became aware of device deficiency
- Deviations
 - Reason for deviation

10.11 Deviation Handling

A study deviation is defined as an event within a study that did not occur according to the CIP or the CTA.

Prior approval by Medtronic is expected in situations where the investigator anticipates, contemplates, or makes a conscious decision to deviate. Prior approval is not required when a deviation is necessary to

Medtronic Business Restricted

China CIED 3.0T MRI Performance Study Clinical Investigation Plan

MDT23009

Version 2.0

Page 27 of 60

Medtronic

protect the safety, rights or well-being of a subject in an emergency or in unforeseen situations beyond the investigator's control (e.g. subject failure to attend scheduled follow-up visits, inadvertent loss of data due to computer malfunction, inability to perform required procedures due to subject illness).

For medically justifiable conditions which preempt a subject's ability to complete a study-required procedure, it may be permitted to report only one deviation which will apply to all visits going forward. This may also apply for other unforeseen situations (e.g. the subject permanently refuses to complete a study required procedure and the data will not contribute to the primary end point analysis). However, prior approval from Medtronic is required for such situations.

All study deviations must be reported on the CRF regardless of whether medically justifiable, pre-approved by Medtronic, an inadvertent occurrence, or taken to protect the subject in an emergency. Multiple deviations of the same type at the same visit may be reported on one case report form.

In the event the deviation involves a failure to obtain a subject's consent, or is made to protect the life or physical well-being of a subject in an emergency, the deviation must be reported to the EC as well as Medtronic within five (5) working days. Reporting of all other study deviations should comply with EC policies and/or local laws and must be reported to Medtronic as soon as possible upon the study site becoming aware of the deviation. Reporting of deviations must comply with EC policies, local laws, and/or RA requirements. Refer to Investigator Reports, Table 10 for geography-specific deviation reporting requirements and timeframes for reporting to Medtronic and/or RAs.

Medtronic is responsible for analyzing deviations, assessing their significance, and identifying any additional corrective and/or preventive actions (e.g. amend the CIP, conduct additional training, terminate the investigation). Repetitive or serious investigator compliance issues may result in initiation of a corrective action plan with the investigator and study site, and in some cases, may necessitate suspending enrollment until the problem is resolved or ultimately terminating the investigator's participation in the study. Medtronic will provide study site-specific reports to investigators summarizing information on deviations that occurred at the investigational study site on a periodic basis.

Examples of study deviations include but are not limited to:

- Failure to obtain proper IC
- Failure to collect required study data
- Inclusion/exclusion criteria not met
- Missing required device interrogation files
- Missing visit

10.12 Subject Exit, Withdrawal or Discontinuation

10.12.1 Study Exit

A study exit eCRF is required for all subjects, can be performed as remote or on site. Prior to exiting a subject from the study, it is recommended to follow the subject until all ongoing system and/or procedure related AEs are resolved or unresolved with no further actions planned. Following exit, subjects will continue to receive standard medical care. Upon exiting from the study, no further study data will be collected or no further study visits will occur for the subject. All data available through the time of the subject's exit will be used for analysis.

Medtronic Business Restricted

Subjects are urged to remain in the study as long as possible but may be exited from the study for any of the following situations:

- Study completed
- Subject lost to follow-up
- Subject death
- Subject did not meet inclusion/exclusion criteria
- Subject did not provide consent
- Subject chooses to withdraw (e.g., consent withdrawal, relocation to another geographic location)
- Investigator deems withdrawal necessary (e.g., medically justified, inclusion/exclusion criteria not met, failure of subject to maintain adequate study compliance)

The following information is required to be collected at study exit:

- Reason for exit

If discontinuation is because of safety or lack of effectiveness, the subject shall be asked to be followed for collecting safety data outside the clinical investigation.

10.12.2 Study Completed

All subjects at the completion of the last enrolled subject 1 month follow-up visit will be exited from the study.

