Inclusion/Exclusion Criteria	
Inclusion Criteria
 
• Subjects who were implanted with an SureScan system CIED (including device and lead) over 6 weeks at the time of signing ICF.• Subjects who are able and willing to undergo elective MRI scanning without sedation.• Subjects who were implanted an SureScan system CIED in the pectoral region.• Subjects who are geographically stable and available for follow-up at the study site for the length of the study.• Subjects who are at least 18 years of age (or older, if required by local law). 
Exclusion Criteria
 
• Subjects who require a legally authorized representative to obtain informed consent.• Subjects with abandoned or capped leads.• Subjects who require an indicated MRI scan, other than those specifically described in the China CIED 3.0T MRI performance study, before the 1-month post-MRI follow-up.• Subjects with a non-MRI compatible device (such as neurostimulators) or material implant (e.g., non-MRI compatible sternal wires, neurostimulators, biostimulators, metals or alloys).• Subjects with medical conditions that preclude the testing required by the CIP or limit study participation.• Subjects who are enrolled or intend to participate in another clinical trial (of an investigational drug or device, new indication for an approved drug or device, or requirement of additional testing beyond

Medtronic Business Restricted

China CIED 3.0T MRI Performance Study Clinical Investigation Plan

MDT23009

Version 2.0

Page 12 of 60

Medtronic

	
standard clinical practice) during the SureScan study. Co-enrollment in concurrent trials is only allowed when documented pre-approval is obtained from the Medtronic study manager.
 
 Female patient who is pregnant, or of childbearing potential and not on a reliable form of birth control. Women of childbearing potential are required to have a negative pregnancy test within seven (7) days prior to MRI scan.
Study Procedures and Assessments	<pre> graph TD Enrollment[Enrollment] --> Baseline[Baseline] Baseline --> MRIVisit[3.0 T MRI visit] Baseline --> PostMRI[1-month post-MRI follow up] MRIVisit --> PreMRI[Pre-MRI check] PreMRI --> MRI[MRI scan] MRI --> PostMRI[Post-MRI check] PostMRI --> Exit[Exit] </pre>

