6.1 Duration

The expected study duration is approximately 9 months, representing 7 months of enrollment and 2 months of subject follow-ups. The duration of individual subject participation will vary based on timing of site activation and their enrollment.

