12.1 Adverse Events

AE definitions are provided in Table 7. All AEs will be collected throughout the study duration, starting at the time of signing the IC.

Reporting of these events to Medtronic will occur on an AE Form. Each event must be reported separately. Documented pre-existing conditions are not considered AEs unless the nature or severity of the condition has worsened.

The completed AE CRF must be submitted to Medtronic as soon as possible.

Any medication/treatment associated with the treatment of an AE must be reported.

Subject deaths are also required to be reported. Refer to Section 12.5 for Subject Death collection and reporting requirements.

In addition, further classification of the relationship will be done by the investigator according to the following parameters:

Table 6 Adverse events parameters

Not Related	
Relationship to the device or procedures can be excluded when:
 
the event has no temporal relationship with the use of the device or procedurethe event does not follow a known response pattern to the device (if the response pattern is previously known) and is biologically implausible;the discontinuation of device application or the reduction of the level of activation/exposure - when clinically feasible – and reintroduction of its use (or increase of the level of activation/exposure), do not impact on the event;the event involves a body-site or an organ not expected to be affected by the device or procedure;the event can be attributed to another cause (e.g. an underlying or concurrent illness/ clinical condition, an effect of another device, drug, treatment or other risk factors);the event does not depend on a false result given by the device used for diagnosis, when applicable; 
In order to establish the non-relatedness, not all the criteria listed above might be met at the same time, depending on the type of device/procedures and the event.

Possible	The relationship is weak but cannot be ruled out completely. Alternative causes are also possible (e.g. an underlying or concurrent illness/ clinical condition or/and an effect of another device, drug or treatment). Cases where relatedness cannot be assessed or no information has been obtained should also be classified as possible.
Probable	The relationship seems relevant and/or the event cannot reasonably explained by another cause.

Medtronic Business Restricted

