7.10 Safety Evaluation

Adverse events collected from enrolled subjects will be summarized using descriptive statistics. Counts and percentages of subjects experiencing system-related or MRI procedure-related adverse events will be reported, as well as, in the case of system-related events, the specific components of the system to which the event was related. The seriousness of adverse events will also be summarized. Details of individual adverse events will be listed. When deemed necessary, individual adverse events where

center investigator classification on relatedness differs from medical advisor will be identified for reporting.

In addition, the term and center description of individual device deficiencies and whether they could have led to a serious adverse device effect will be reported. Individual deaths (if any) including death classification per center investigator and per medical advisor will also be listed.

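### SAP 7.10 sets no time window, so the system-related, overall and serious AE summaries cover unequal time that depends on enrolment order and recruitment speed

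*Combined protocol and SAP*

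**What the plan says.** - **Exit of completers (CIP 10.12.2):** "All subjects at the completion of the last enrolled subject 1 month follow-up visit will be exited from the study". CIP 6.1 agrees: "The duration of individual subject participation will vary based on timing of site activation and their enrollment".
- **Planned duration (CIP 6.1):** "The expected study duration is approximately 9 months, representing 7 months of enrollment and 2 months of subject follow-ups".
- **AE collection (CIP 12.1):** "All AEs will be collected throughout the study duration, starting at the time of signing the IC". CIP 10.12.1 adds: "All data available through the time of the subject's exit will be used for analysis".
- **Visits (CIP Table 4 and section 10.8):** the last scheduled AE assessment and device check is the one-month post-MRI visit. After that, AEs are reported as they occur. The exit form can be completed remotely, and the only item listed as required is the reason for exit.
- **AE reporting (SAP 7.10):** "Adverse events collected from enrolled subjects will be summarized using descriptive statistics", and "Counts and percentages of subjects experiencing system-related or MRI procedure-related adverse events will be reported". Seriousness is summarised too, and individual events are listed. The section gives no time window, no person-time and no split at the scan or at the one-month visit.
- **Definitions (CIP Table 7):** an MRI procedure-related AE can be counted only up to the one-month visit. The system-related categories, including the one for the SureScan feature, have no time limit.

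**The concern.** A percentage of subjects with an event can be interpreted only if the period at risk is known. Here the period runs from consent to a common calendar close-out, so the first subject enrolled is at risk for many more months than the last. The same device performance would give a higher system-related percentage in a slowly recruiting study than in a fast one.

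The summary also pools three kinds of time: before the scan, the month after it with active assessment, and a later stretch without scheduled visits. Enrolled subjects who are never scanned are included. The exclusion for other indicated MRI scans (CIP 9.4) reaches only to the one-month follow-up. A later non-study scan could therefore contribute events to the same system-related count.

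What is at stake is how the general safety table is read. It will stand in the report next to a primary result with a fixed 30-day window, and nothing in SAP 7.10 tells the reader that the periods differ.

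**Working it through.** **Inputs**
- Enrolment period of 7 months and study duration of about 9 months (CIP 6.1).
- 64 subjects enrolled (CIP 14.5).
- Scan on the day of baseline (allowed by CIP 10.6), or within the recommended 30 days (CIP Table 5 footnote).
- One-month visit window of day 30 to day 56 (CIP Table 5); 56/30.4 = 1.84 months.
- Assumption, not in the documents: enrolment is even over the 7 months and the delay to scan is the same for everyone.

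**The plan's own figure.** 7 + 2 = 9 months. The 2 months fit a last subject who is scanned about 30 days after baseline and seen 30 days after that.

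**Range of follow-up under the common close-out.** Time from scan to exit is the close-out month minus the enrolment month minus the delay to scan. With enrolment spread over months 0 to 7 (mean 3.5):

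| Close-out | Consent to scan | Consent to exit, months (mean) | Scan to exit, months (mean) | Share of consent-to-exit time after the first post-scan month |
|---|---|---|---|---|
| Month 8 | same day | 1 to 8 (4.5) | 1 to 8 (4.5) | 3.5/4.5 = 78% |
| Month 9 | 1 month | 2 to 9 (5.5) | 1 to 8 (4.5) | 3.5/5.5 = 64% |
| Month 9 | same day | 2 to 9 (5.5) | 2 to 9 (5.5) | 4.5/5.5 = 82% |

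**Average time beyond the own one-month visit.** For 64 uniform enrolment times over A months, the last is expected at A × 64/65 and the mean is A/2. For A = 7: 7 × 64/65 − 3.5 = 6.89 − 3.50 = 3.39 months. As a share of post-scan time:
- visit at day 30: 3.39/(3.39 + 1.00) = 77%
- visit at day 56: 3.39/(3.39 + 1.84) = 65%

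**Dependence on recruitment speed (illustrative values of A).** At A = 4, 4 × 64/65 − 2 = 1.94 months. At A = 10, 10 × 64/65 − 5 = 4.85 months. The time at risk after the one-month visit is thus set by recruitment, which has nothing to do with the device or the scan.

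**What this could do to a percentage.** The documents give no AE rate, so constant monthly rates λ are assumed. The one-month percentage is 1 − exp(−λ). With scan-to-exit time even on 1 to 8 months, the to-exit percentage is 1 − [exp(−λ) − exp(−8λ)]/(7λ). For λ = 0.05:
- one month: 1 − 0.9512 = 4.9%
- to exit: 1 − (0.9512 − 0.6703)/0.35 = 19.7%, about 4 times as high

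| Assumed rate per month | One month | To exit, 1 to 8 months | To exit, 2 to 9 months |
|---|---|---|---|
| 1% | 1.0% | 4.4% | 5.3% |
| 2% | 2.0% | 8.5% | 10.3% |
| 5% | 4.9% | 19.7% | 23.6% |
| 10% | 9.5% | 34.9% | 41.1% |

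The ratio runs from about 3.7 to 5.4. If fewer events are reported once scheduled visits stop, the observed ratio would be smaller.

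**The case against.** The strongest reply is that SAP 7.10 never claims to measure safety within one month. That is the job of the primary endpoint, which has its own 30-day window. SAP 7.10 is a general descriptive summary, individual events are listed, and the SAP says that it does not limit the analyses in reports. For 64 subjects the timing could be recovered from the listing. The common close-out is disclosed, and CIP 6.1 says openly that participation varies.

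Most of this stands, and it limits the point. It does not remove it: the one system-related percentage that SAP 7.10 commits to still has no stated period, and neither do the overall and seriousness summaries.

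Several further points on the plan's side also stand:
- MRI procedure-related AEs are closed off at the one-month visit by their definition.
- The time after that visit is not unobserved. AEs remain reportable, unscheduled visits collect AE and device data (CIP 10.9), and the medical advisor reviews all AEs at regular intervals (CIP 13). It is correctly described as time without scheduled visits.
- SAP 7.10 attaches percentages to system-related and MRI procedure-related AEs. For seriousness it promises only a summary.
- The 77% and 65% are shares of time under assumed accrual, not shares of events.

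**Conclusion.** The point holds for system-related, overall and serious AEs. Under the common close-out these summaries cover about 1 to 8 months after the scan (up to 9 with same-day scans and close-out at month 9), plus pre-scan time and never-scanned subjects. On average 3.39 months per completer fall after the last scheduled visit. These sizes rest on even enrolment over 7 months and an equal delay to scan. The effect on any percentage is illustrative only, because the documents give no AE rate.

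Three stronger readings are tempting, and the documents do not support them:
- **That all AE percentages in the SAP, or the primary safety result, are distorted.** Table 7 bounds the MRI procedure-related AEs, and the primary endpoint has a 30-day window. Alpha, power and sample size do not change.
- **That the CIP contradicts itself on exit.** The only evidence is the machine-read synopsis flow, "PostMRI --> Exit[Exit". The node name in it carries two labels, the immediate post-MRI check and the one-month follow-up, so it cannot show which step leads to exit. A flow chart also shows sequence, not calendar time. The text of 6.1 and 10.12.2 is consistent.
- **That each subject should exit at their own one-month visit.** CIP 10.12.1 stops study data collection at exit. New late AEs would then be lost, not merely moved out of the main table.

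This is a gap in descriptive safety reporting, and closing it is a cheap improvement.

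**What to change.** Leave the exit rule in CIP 10.12.2 unchanged. In SAP 7.10, tabulate system-related, overall and serious AEs by period, assigning each event by its onset date:

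1. Consent to scan, with enrolled subjects as denominator.
2. Scan to the subject's own one-month visit, with scanned subjects as denominator. This is the main post-scan safety table.
3. After that visit to exit, reported separately or as a listing and marked as collected without scheduled visits.

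Period 2 varies with the visit date (day 30 to 56, or later for a late visit), but it no longer depends on enrolment order or on when the last subject is recruited.

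The cost is a short addition to SAP 7.10 and one extra table split. No new data are needed, because the 30-day primary endpoint and the visit-window checks already require event, scan and visit dates. The downside is that the main table no longer includes late reports; they stay in the separate table or listing.
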